7.2 Exclusion Criteria

Any subject who meets any of the following criteria will not qualify for entry into the study:

1. The subject has suspected hypotension with associated physical findings, such as dizziness postural, facial pallor, or cold sweats based on evaluation/physical examination at Screening, on the day before the study drug administration (Day -1) in Period 1, or up to the study drug administration in Period 1.
2. The subject has received any study drug within 16 weeks (112 days) prior to the study drug administration in Period 1.
3. The subject has received TAK-536 or TAK-491 in a previous clinical study or as a therapeutic agent.
4. The subject has uncontrolled, clinically significant neurologic, cardiovascular, pulmonary, hepatic, renal, metabolic, gastrointestinal, or endocrine disease or other abnormality, which may impact the ability of the subject to participate or potentially confound the study results.
5. The subject has a hypersensitivity to any component of the formulation of TAK-536 or any ARB.

6. The subject has a positive urine drug result for drugs of abuse (defined as any illicit drug use) at Screening.
7. The subject has a history of drug abuse (defined as any illicit drug use) or a history of alcohol abuse within 2 years prior to the Screening visit or is unwilling to agree to abstain from alcohol and drugs throughout the study.
8. The subject has taken any excluded medications, supplements, dietary products or food products during the time periods listed in Section 7.3.
9. The subject has any current or recent (within 6 months prior to the start of the study drug administration in Period 1) gastrointestinal diseases that would be expected to influence the absorption of drugs (ie, a history of malabsorption, esophageal reflux, peptic ulcer disease, erosive esophagitis, frequent [more than once per week] occurrence of heartburn, or any surgical intervention).
10. The subject has a history of cancer, except the basal cell carcinoma which has been in remission for at least 5 years prior to Day 1 of Period 1.
11. The subject has a positive test result for hepatitis B virus surface antigen (HBsAg), hepatitis C virus (HCV) antibody, human immunodeficiency virus (HIV) antibody/antigen, or serological reactions for syphilis at Screening.
12. The subject has poor peripheral venous access.

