7.3 Excluded Medications, Supplements, Dietary Products

Use of excluded agents (prescribed or over-the-counter [OTC] drugs) and dietary products is listed in [Table 7.a](#).

Table 7.a Excluded Medications, Supplements, and Dietary Products

From 4 weeks (28 days) before the study drug administration in Period 1 to the day of discharge (Day 3) in Period 2	From 72 hours before the study drug administration to the day of discharge (Day 3) in each period
Concomitant drugs (prescribed or OTC drugs) Vitamins, Chinese herbal medicines, dietary products containing St. John’s wort, Korean ginseng, kava kava, ginkgo, or melatonin	Foods and beverages containing grapefruit (juice, pulp), Seville-type (sour) oranges, pineapple (juice, pulp), caffeine or alcohol
OTC: over-the-counter	

Subjects must be instructed not to take any medications including OTC products, without first consulting with the investigator or sub-investigator. Use of prohibited concomitant drugs will be allowed when the investigator or sub-investigator deems it necessary to use any of the concomitant drugs for reasons including treatment of an AE.

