7.4.2 Activity

Smoking is not allowed during the study period.

Supine position is not allowed for 4 hours after the study drug administration, unless it is required for examinations. The subjects will engage in 15 minutes of light exercise a day during hospitalization.

The subjects should abstain from excessive exercise after signing of the informed consent until completion of follow-up examination in Period 2. The subjects will be instructed to lead the same kind of daily life in Period 2 as that in Period 1, and lead a regular life throughout the washout period between the study drug administrations.

Blood donation is not allowed for at least 12 weeks after the final examination of this study. The investigator or sub-investigator will instruct the subjects on the prohibition of blood donation.

If a subject visits another medical institution during the study period, the investigator or sub-investigator should be informed of the circumstances and therapy in advance whenever possible, and should communicate to the medical institution about the subject's participation in the study.

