## **7.2 Analysis Sets**

- Pharmacokinetic (PK) Analysis Set: All subjects who received the study drug, completed the minimum protocol-specified procedures without any major protocol deviations, and were evaluable for pharmacokinetics
  - Any subject who meets the following criteria will be excluded from this analysis set:
    - 1) Deviations of protocol entry criteria
      - Deviations of inclusion criteria
        - Inclusion criteria 3, 4, and 5
        - Deviations of exclusion criteria
          - Exclusion criteria 2, 4, 6, 7, 8, 9, 10, 11, and 17

- 2) Deviations related to treatment procedure or dose
  - Deviations related to dose
    - Deviations of dosage

Subjects who received a dose of the study drug other than the doses specified in the protocol
    - Deviations of regimen
      - Deviations of dosing interval (number of days for washout)

Subjects who received the study drug in Period 2 without undergoing a washout period of more than 6 days after the study drug administration in Period 1
      - Deviations of dosing conditions

Subjects who did not orally receive a single dose of any study drug under treatment conditions specified in that treatment period
- 3) Deviations concerning excluded medication or therapy
  - Deviations concerning concomitant medications
    - Administration of excluded medication

Subjects who consumed drugs (prescribed or over-the-counter drugs) described in Table 7.a “Excluded Medications, Supplements, and Dietary Products” listed in the protocol section 7.3 within the given time
- 4) Deviations concerning pharmacokinetic measurements
  - Plasma drug concentration
    - No conduct/missing of examinations and assessments concerning pharmacokinetic variables

Subjects whose plasma drug concentration data of TAK-536 was missing or not used at more than 1 visit
- 5) Others
  - Matters of subject management
    - Matters concerning foods and beverages
      - Subjects who consumed meals other than the provided meals during hospitalization
      - Subjects who consumed meals within 10 hours before the study drug administration
      - Subjects who consumed meals within 4 hours after the study drug administration
      - Subjects who consumed beverages other than the drink provided as a part of breakfast (under fed condition) and water (200 mL)

taken with the study drug from 1 hour before to 4 hours after the study drug administration

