Subjects who consumed foods described in Table 7.a “Excluded Medications, Supplements, and Dietary Products” listed in the protocol section 7.3 within the given time

Matters concerning smoking

Subjects who smoked during hospitalization

Matters concerning body position

Subjects who took a supine position for 4 hours after the study drug administration, unless it was required for examination.

- Safety Analysis Set: All subjects who received the study drug

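### Read literally, SAP 7.2 drops a whole subject from the PK analysis set for drug use that the protocol permits, or for lying down because of an adverse event, with no test of PK relevance and no sensitivity analysis

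*SAP*

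**What the plan says.** - **Force of the list.** SAP 7.2 introduces its criteria with "Any subject who meets the following criteria will be excluded from this analysis set". The unit is the subject, so both periods go.
- **Drugs.** Item 3, headed "Deviations concerning excluded medication or therapy", lists "Subjects who consumed drugs (prescribed or over-the-counter drugs) described in Table 7.a" of protocol 7.3 within the stated time. It does not ask why the drug was taken or whether it could alter TAK-536 concentrations.
- **Window.** The drug column of protocol Table 7.a runs "From 4 weeks (28 days) before the study drug administration in Period 1 to the day of discharge (Day 3) in Period 2", without a break across the washout.
- **Permission.** The text under the same table says: "Use of prohibited concomitant drugs will be allowed when the investigator or sub-investigator deems it necessary". It names AE treatment among the reasons.
- **Posture.** Protocol 7.4.2 says "Supine position is not allowed for 4 hours after the study drug administration, unless it is required for examinations". SAP 7.2 item 5 turns this into an exclusion: "Subjects who took a supine position for 4 hours after the study drug administration, unless it was required for examination". Neither mentions lying down because of an AE.
- **Use of the set.** SAP 7.9.1.3 runs the food-effect ANOVA on the PK analysis set only. Excluded subjects still appear in the individual plots and listings (SAP 7.9.1.4 and 7.9.1.5). No sensitivity analysis is planned.
- **Replacement.** Under protocol 7.8, subjects who discontinue after Period 1 dosing are not replaced. No replacement is described for a subject later excluded from the PK set.

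**The concern.** The protocol permits an action and the SAP, as worded, then discards the subject's primary data because of it. Protocol 11.1.1.2 removes subjects from the PK set for major deviations, and use that protocol 7.3 allows is hard to call one. Yet SAP 7.13 says that its plan is the same as the protocol's.

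The trigger can be an adverse event or its treatment, so missing primary data may be linked to tolerability. The drug is an antihypertensive. Exclusion criterion 1 in protocol 7.2 screens out "suspected hypotension with associated physical findings, such as dizziness postural, facial pallor, or cold sweats" up to the first dose, so a subject who needs to lie down after dosing is foreseeable.

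In a trial of 12, each lost subject costs precision. In an open-label trial, a decision on how to read the rule should not wait until concentrations can be seen.

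**Working it through.** The documents give no power, effect size, variability or margin for the 12 subjects, so there is no stated figure to reproduce. The check is of timing, precision and possible bias.

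**1. Timing of the drug window against the samples**

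- Minimum span: 28 days before dose 1, plus 6 days between doses, plus 2 days to Day 3 of Period 2 = 36 days. Of these, 28 precede any dose; about 6 + 2 = 8 days follow the first dose and could involve treatment of a post-dose event.
- Protocol 7.4.1 puts the fed dose at about 09:00, so the 48-hour sample falls at about 09:00 on Day 3 (±15 minutes, Appendix B). The ban covers the day of discharge. If that means until midnight, up to about 15 hours of it follow the last concentration of the study.
- Share of the window: 28×24 + 6×24 + 48 + 15 = 879 hours; 15/879 = 1.7%.
- Between the Period 1 48-hour sample and the Period 2 dose there are at least 144 − 48 = 96 hours. A drug first taken then cannot affect Period 1 concentrations. Whether it can affect Period 2 depends on the drug and the timing, which the rule does not ask.

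**2. Precision**

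For a 2×2 crossover, the 90% half-width on the natural-log scale is

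t(0.95, nA+nB−2) × s_w × √[½(1/nA + 1/nB)].

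At the same s_w:

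- 6+5 against 6+6: √[(1/6+1/5)/(1/6+1/6)] × t(0.95, 9)/t(0.95, 10) = 1.0488 × 1.0114 = 1.061, about 6% wider.
- 5+5 against 6+6: 1.0954 × (1.860/1.812) = 1.124, about 12% wider.

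The documents give no within-subject CV. With assumed values, s_w = √ln(1+CV²) and a true ratio of 1.00, the 90% intervals are:

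| Assumed CV | 12 subjects | 11 (5+6) | 10 (5+5) |
|---|---|---|---|
| 15% | 0.895–1.117 | 0.890–1.124 | 0.883–1.132 |
| 20% | 0.864–1.158 | 0.856–1.168 | 0.848–1.179 |
| 30% | 0.805–1.243 | 0.794–1.259 | 0.783–1.277 |

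**3. How often**

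The rate of such exclusions is not in the documents. If each subject independently has chance p, the chance of losing at least one is 1 − (1−p)^12: 22% at p = 2%, 46% at 5%, 72% at 10% and 93% at 20%. All four values of p are assumptions.

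**4. Bias**

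Exclusion removes both of a subject's periods, so neither condition is thinned out relative to the other. The fed-minus-fasted log contrast shifts only if exclusion is related to the subject's own contrast. As an extreme bound, suppose that the one subject lost has the largest ratio of the 12. The expected maximum of 12 standard normals is 1.63 (by simulation), and the SD of a subject's log ratio is √2 × s_w. Ignoring the period adjustment, the geometric mean ratio is multiplied by exp(−1.63 × √2 × s_w / 11): 0.969 at CV 15%, 0.959 at 20% and 0.940 at 30%. This is a worst case, not a prediction.

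**The case against.** The strongest reply is that exclusion is not automatic. Item 3 is headed as deviations, and use that protocol 7.3 allows is arguably not one. The list cannot be applied word for word anyway: its item on meals in the 10 hours before dosing is not limited to the fasted condition and would remove everyone dosed fed. SAP 7.3.4.2 also refers to a separate list of subject evaluability assignments, which may settle individual cases. The supine wording could mean lying down for the full 4 hours. These readings are possible, but neither document adopts any of them, so the ambiguity stands.

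A reader might infer more than the text supports:

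- *That the fed or fasted condition with the higher Cmax is selectively removed.* It is not; whole subjects go. The documents do not say that AEs track exposure at this dose.
- *That a drug taken on Day 4 of Period 1 is too late to matter.* Day 6 of Period 1 may coincide with Day −1 of Period 2, so Day 4 can fall three days before the second dose. Only use after the final Period 2 sample is certainly too late.
- *That 36 days are at issue.* Most of that span precedes dosing and is an entry matter under exclusion criterion 8.
- *That hypotension is ranked as the leading safety concern.* The numbering of entry criteria states no ranking.
- *That the rule sets care of the subject against the data.* Protocol 6.2.6 gives urgent safety procedures precedence, and protocol 12.2 allows deviation to remove an immediate hazard.

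It is also fair that the loss of precision is modest in a trial with no power basis and no equivalence margin, and that excluded subjects remain visible in plots and listings.

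**Conclusion.** The point holds as a gap in the SAP's wording. Taken literally, SAP 7.2 excludes subjects for drug use that protocol 7.3 permits, for drug use on Day 3 of Period 2 after the last sample, and possibly for lying down because of an AE. Nothing planned would show the effect on the food-effect estimate.

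The firm part of the size is the 6% or 12% widening for one or two lost subjects, which assumes only an unchanged within-subject SD. The interval limits, exclusion rates and bias bound rest on assumed values. Bias is possible but not shown. The part that is certainly too late to matter is confined to the remainder of one day. This is a cheap improvement, not a flaw that undermines the trial.

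**What to change.** In SAP 7.2:

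1. State that drugs first taken after the Period 2 48-hour sample do not exclude a subject.
2. For drug use allowed under protocol 7.3, and for supine position because of an AE, exclude only if the drug or posture and its timing are judged able to alter TAK-536 PK. Make and record that judgement before database lock and without sight of the concentrations. Posture needs the same review as drugs, because any effect on absorption does not depend on the reason for lying down.
3. Repeat the food-effect ANOVA on all dosed subjects with evaluable PK, keeping those excluded under step 2, and once more without any subjects retained under step 2.
4. Say whether the supine criterion means any time within the 4 hours or the whole of it.

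Reconcile SAP 7.2 with protocol 7.3 and 7.4.2 on how these cases are classified. No clinical rule needs to change for this, and clinical handling stays with the sponsor and the investigator. The cost is SAP wording, a case-by-case judgement before lock for any affected subject, and a small number of extra model runs.

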9.3.1 PK Measurements

The following PK parameters of unchanged TAK-536 will be determined from the plasma concentration-time profile up to 48 hours after the study drug administration based on non-compartmental analysis. Actual sampling times, instead of scheduled sampling times, will be used in all PK computations.

The following PK parameters will be calculated from plasma concentrations of TAK-536, unless otherwise specified:

Symbol/Term	Definition
Plasma	
AUC _{last}	Area under the plasma concentration-time curve from time 0 to time of the last quantifiable concentration.
AUC _∞	Area under the plasma concentration-time curve from time 0 to infinity.
C _{max}	Maximum observed plasma concentration (observed value).
t _{max}	Time of first occurrence of C _{max} (observed value).
MRT	Mean residence time.
λ _z	Terminal disposition phase rate constant.
t _{1/2z}	Terminal disposition phase half-life.
CL/F	Apparent clearance after extravascular administration.
V _{z/F}	Apparent volume of distribution during the terminal disposition phase after extravascular administration.

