#### 7.1.3 Definition of Study Visit Windows

For items of examinations, observations, and assessments described below, evaluable data (i.e., non-missing data) will be handled according to the following rules.

Evaluable data within the visit window will be used. If more than one evaluable data exist within the same visit window, the examinations, observations, and assessments with the closest Study Time to the scheduled Study Time will be used. If there are two evaluable equidistant to the scheduled Study Time, the later data will be used. The size of difference from the Study Time will be determined based on the total Study Time in each time interval (hour).

For items from examinations, observations, and assessments other than those described below, evaluable data will be handled as data at the corresponding visit based on the visits specified in the case report form. However, among the visits specified in the case report form, if the follow-up examination in Period 1 (Day 6) and the examination on the day before the study drug administration (Day -1) in Period 2 were conducted on the same day and only the evaluable data exists from either the follow-up examination (Day 6) for Period 1 or the day before the study drug administration (Day -1) for Period 2, that data will be handled though it were obtained at both visits.

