### *7.8.4.2 Handling of Dropouts or Missing Data*

Missing test results or data determined to be non-evaluable according to this Statistical Analysis Plan will not be used for hypothesis testing and estimations.

Values below the lower limit of quantification in drug concentrations and laboratory test values will be treated as zero, and values above the upper limit of quantification in laboratory test values will be treated as the upper limit of quantification.

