#### 7.9.1.3 Assessment of Food Effect

Analysis Set: PK Analysis Set  
Analysis Variable(s): Pharmacokinetic Parameters of TAK-536  
Cmax tmax AUClast  
AUCinf t1/2z MRTlast,ev  
MRTinf,ev Lambda z CL/F  
Vz/F  
Analysis Method(s): The following analysis will be performed for the above analysis variables.

- (1) The difference in the least square means between treatment conditions (single oral dose under fed condition – single oral dose under fasted condition) and the two-sided 90% confidence interval will be provided using a crossover ANOVA model. The ANOVA model will include log-transformed (natural log) analysis variables other than tmax as the dependent variable, and treatment condition, treatment group, and period as independent variables.
- (2) The difference in the least square means between treatment conditions (single oral dose under fed condition – single oral dose under fasted condition) and the two-sided 90% confidence interval will be provided using a crossover ANOVA model. The ANOVA model will include non-natural log-transformed tmax as the dependent variable, and treatment condition, treatment group, and period as independent variables.

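### Could two slightly mistimed blood draws remove a subject from the food-effect ANOVA under SAP 7.2 item 4?

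*SAP*

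**What the plan says.** SAP 7.2 lists grounds for excluding a subject, not a single period, from the PK analysis set. Item 4 has the sub-heading "No conduct/missing of examinations and assessments concerning pharmacokinetic variables" and the criterion "Subjects whose plasma drug concentration data of TAK-536 was missing or not used at more than 1 visit".

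SAP 7.1.3 says "Evaluable data within the visit window will be used" and treats evaluable as meaning non-missing: "evaluable data (i.e., non-missing data) will be handled according to the following rules". Plasma concentration is the only item in the window table (Table 7.a). Its postdose limits are ±0.083 h for 0.5 to 12 h and ±0.250 h for 16, 24 and 48 h, which are the ±5 and ±15 minutes of Protocol Appendix B. SAP 7.8.4.2 adds that "data determined to be non-evaluable according to this Statistical Analysis Plan will not be used for hypothesis testing and estimations".

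The food-effect ANOVA in SAP 7.9.1.3 is headed "Analysis Set: PK Analysis Set". Protocol 9.3.1 says of the parameters: "Actual sampling times, instead of scheduled sampling times, will be used in all PK computations". SAP 7.3.4.2 classifies the handling of subjects by a List of Subject Evaluability Assignments, a separate document. SAP 7.13 declares the SAP's analysis to be the same as the protocol's.

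**The concern.** Item 4 names data that are not used separately from data that are missing, and *used* is also the word by which SAP 7.1.3 selects in-window data. A programmer could conclude that a concentration measured 6 minutes late at 2 h is not used, and that a second such draw removes the subject from both periods of the analysis that answers the primary objective. That seems harsh when the non-compartmental calculation works from the recorded time and can take a late sample as it is. Two analysts could also count differently, one per period and one over both.

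At stake is precision in a study of 12. No ANOVA that keeps such a subject is planned. SAP 7.9.1.4 and 7.9.1.5 would still plot and list the subject's data.

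**Working it through.** There is no plan figure to reproduce: SAP 6.0 states that the 12 subjects have no statistical basis. The check takes the text, then the size of the loss, then the size of the timing error, then the frequency.

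**1. The readings.**
- Wide: not used includes measured but out of window (SAP 7.1.3 with Table 7.a).
- Narrow: only samples not taken or missing. The sub-heading supports this. So does SAP 7.8.4.2, because non-evaluable there means missing under SAP 7.1.3.
- Intermediate: a sample was taken but its result was set aside for sample or assay reasons. This fits the sub-heading and gives the extra words a meaning of their own.

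The text does not decide between them. Table 7.a assigns values to visits, which the by-time-point summaries of SAP 7.9.1.1 need. A non-compartmental calculation on actual times does not need it. Protocol 9.3.1 and SAP 7.13 therefore point towards using measured values, though neither says outright that every out-of-window value enters.

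**2. Precision lost.** For a 2×2 crossover with within-subject error, the 90% half-width on the log scale is t(0.95, n1+n2−2) × s × √[½(1/n1+1/n2)]. The ratio to 6+6 does not depend on s.
- 6+5: (1.8331/1.8125) × √1.1 = 1.061, so 6.1% wider.
- 5+5: (1.8595/1.8125) × √1.2 = 1.124, so 12.4% wider.

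SAP 7.9.1.3 lists treatment condition, treatment group and period, with no subject term. Taken literally, the error degrees of freedom are 20, 18 and 16, and the two figures become 5.4% and 10.9%.

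Illustration with an assumed within-subject CV of 20% and a ratio of 1: s = √ln(1.04) = 0.198 and the half-width is 1.8125 × 0.198 × √(1/6) = 0.1465. The interval is 0.864 to 1.158 with 12 subjects and 0.856 to 1.168 with 11.

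**3. Timing error.** The half-life is about 13 h (Protocol 6.2.4), so ke = ln2/13. The rest assumes a one-compartment curve with first-order absorption. The documents give no tmax, so the peak is placed at 1 to 4 h (ka 4.49 to 0.70 per h).
- Terminal phase, before actual times are applied: 1 − exp(−ke × 0.1) = 0.53% at 6 minutes late; 1 − exp(−ke × 0.267) = 1.41% at 16 minutes late.
- Peak: a draw 6 minutes off lowers observed Cmax by 0.02% to 0.14%.
- AUC to 48 h: two samples 6 minutes late, at their actual times, change it by about 0.01% (ka 0.5 to 2 per h).
- Absorption phase: the 0.5 h concentration changes by +3.8% to +15.8% if drawn 6 minutes late, and by −6.3% to −17.1% if 6 minutes early.

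The parameters are hardly touched. The early time-point concentrations are affected, and actual times do not correct them in a by-visit summary.

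**4. Frequency.** The documents give no rate. Assuming independent draws with out-of-window probability p, the chance that a subject has at least 2 of the 30 postdose samples out of window is:

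| p | Over both periods |
|---|---|
| 0.1% | 0.04% |
| 1% | 3.6% |
| 5% | 45% |

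Counting per period at p = 1% gives 1.9%. The range is too wide to support any single expected loss.

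**The case for a change.** The best argument for a change is that it is cheap and timely. A few words would define the term and the count basis, so that who enters the primary analysis is not decided with concentrations in view in an open-label study of 12. A rounding point adds to this: if study time is kept to four decimals, a 0.5 h sample drawn exactly 5 minutes early (0.4167 h) falls below the 0.417 limit although Appendix B allows it. At three decimals it falls inside.

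It stands that the term is undefined, that the count basis is unstated, and that the wide reading is possible. It does not follow that the plan needs correcting. The evaluability list cited in SAP 7.3.4.2 is a natural place for such detail and cannot be inspected here. The wide reading is also defensible. An out-of-window draw already departs from Appendix B, the PK set is meant to be free of major deviations, and the rule tolerates one such visit. Plasma concentrations are part of the primary endpoint and are summarised on the same set, so the shift at 0.5 h gives a strict timing rule some purpose. Replacing a fixed count with a judgement of usability would bring in discretion of its own.

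**Conclusion.** No change follows. This is an undefined term and an unstated count basis, which analysts can settle sensibly from the sub-heading of item 4, the actual-time rule in Protocol 9.3.1 and the evaluability list. If the strictest reading were applied and a subject met it, the estimate would remain valid and its 90% interval would be about 6% wider for one subject lost, or about 12% wider for one lost per sequence. These widths assume within-subject error; under the model as literally listed they are about 5% and 11%. No decision rule would change, because the documents set no margin or precision target.

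The frequency is unknown and may be zero: sampling is inpatient at one site, and Protocol 6.2.6 puts the blood draw ahead of ECG and vital signs. The timing-error figures rest on an assumed one-compartment curve and support both sides, with negligible effect on AUC and Cmax but roughly 4% to 17% on a 0.5 h concentration drawn 6 minutes off time.

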7.4 Diet, Fluid, Activity

7.4.1 Diet and Fluid

On the day of blood collection for laboratory tests (screening examination and follow-up examinations), the subjects must finish the last meal at least 8 hours before visiting the study site.

During hospitalization, the subjects take given meals and are not allowed to take any other food. Meal menus will be the same for each period.

On the day of the study drug administration (Day 1) under fasted condition in each period, the subjects must fast from at least 10 hours before the study drug administration to 4 hours after the study drug administration. The subjects will be instructed to have lunch at 13:00 and dinner at 19:00 (approximate time). Under fed condition, the subjects will have breakfast at 8:30 (approximate time) and will have the study drug at 30 minutes after starting the breakfast. The subjects will have lunch at 13:00 and dinner at 19:00 (approximate time). On the days other than the above, the subjects will be instructed to have breakfast at 9:00, lunch at 13:00 and dinner at 19:00 (approximate time). The subject can choose not to have breakfast on Day 3 (the day of discharge).

Excessive drinking and eating should be avoided during the entire study period including follow-up examinations.

On the day of the study drug administration (Day 1) for both periods, the subjects should be prohibited from drinking any liquid from 1 hour before to 4 hours after the study drug administration, with the exception of drink provided as a part of breakfast (under fed condition) and water (200 mL) taken with the study drug.

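### The SAP's 4-hour post-dose meal exclusion names no condition, so a fed subject who follows the protocol's meal schedule can be removed from the PK analysis set

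*SAP*

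**What the plan says.** SAP 7.2 lists deviations that remove a subject from the PK analysis set. The list is mandatory: "Any subject who meets the following criteria will be excluded from this analysis set". Item 5, on foods and beverages, contains two adjacent meal criteria, "Subjects who consumed meals within 10 hours before the study drug administration" and "Subjects who consumed meals within 4 hours after the study drug administration". Neither names a treatment condition. The beverage criterion in the same item does make allowance for the fed condition: "Subjects who consumed beverages other than the drink provided as a part of breakfast (under fed condition) and water (200 mL".

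Protocol 7.4.1 ties the food fast to one condition: "On the day of the study drug administration (Day 1) under fasted condition in each period, the subjects must fast". That fast runs from 10 hours before dosing to 4 hours after. For the other condition it says: "Under fed condition, the subjects will have breakfast at 8:30 (approximate time) and will have the study drug at 30 minutes after starting the breakfast". It continues: "The subjects will have lunch at 13:00 and dinner at 19:00 (approximate time". No minimum interval between dose and lunch is set for fed subjects. The only 4-hour post-dose limit on intake that covers both conditions concerns liquids.

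SAP 7.9.1.3 runs the food-effect comparison on the PK analysis set. Protocol 7.8 does not replace subjects who discontinue after dosing in Period 1. SAP 7.13 states that its analysis plan is the same as the protocol's.

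**The concern.** The SAP criterion is wider than the protocol rule it enforces. In the fasted condition the two agree. In the fed condition the SAP penalises an interval that the protocol does not require, and the protocol's nominal schedule lands exactly on the SAP's limit.

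The PK analysis set is defined by the absence of major protocol deviations, yet this criterion can remove a subject who has none. Exclusion is by subject, so a meal-timing trigger in the fed period also discards the fasted period. With 12 subjects, each loss is visible in the precision of the primary comparison. Whether a given subject is lost would turn on his exact dosing minute and the time lunch reached him, not on any breach. The criterion would also have to be interpreted when subjects are assigned to analysis sets, which is a poor time to settle what it means.

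**Working it through.** The plan gives no figure to reproduce here. Protocol 11.3 and SAP 6.0 both say the sample size has no statistical basis.

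**1. Which rule covers which condition**

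| Rule | Fasted | Fed |
|---|---|---|
| Protocol 7.4.1, no food until 4 h postdose | yes | not stated |
| Protocol 7.4.1, no liquid until 4 h postdose (breakfast drink and dosing water excepted) | yes | yes |
| SAP 7.2, excluded if a meal is taken within 4 h postdose | yes | yes (no condition named) |

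The mismatch is confined to the first and third rows of the fed column.

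**2. Nominal gap under the fed condition**

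Inputs from Protocol 7.4.1: breakfast 8:30, dose 30 min after breakfast starts, lunch 13:00, with breakfast and lunch marked as approximate.

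- Dose time = 8:30 + 0:30 = 9:00.
- Gap = 13:00 − 9:00 = 4 h 00 min.

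**3. Gap for other dose times, lunch at 13:00**

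| Dose | Gap (h) | Meets the SAP criterion? |
|---|---|---|
| 8:55 | 4.083 | no |
| 9:00 | 4.000 | only if exactly 4 h counts; the SAP does not say |
| 9:01 | 3.983 | yes |
| 9:10 | 3.833 | yes |
| 9:15 | 3.750 | yes |

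The approximation also works the other way. Lunch at 12:55 after a 9:00 dose gives 3 h 55 min, which meets the criterion.

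**4. Is the 9:10 subject compliant?**

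Breakfast at 8:40 is within an approximate 8:30, dosing is 30 min after breakfast starts, and lunch is at 13:00. He complies with Protocol 7.4.1 provided he drinks nothing until 9:10 + 4 h = 13:10. If he drinks with lunch before then, he breaches the liquid rule and the SAP beverage criterion excludes him for a real deviation. The problem therefore concerns a subject who eats before 4 h but does not drink.

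**5. Cost per subject lost**

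In a 2×2 crossover with *n* subjects, the 90% CI half-width is t(0.95, n−2) × √(2/n) × within-subject SD. With the SD held fixed:

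| n | t(0.95, n−2) | √(2/n) | Product | Relative to n = 12 |
|---|---|---|---|---|
| 12 | 1.812 | 0.408 | 0.740 | 1.00 |
| 10 | 1.860 | 0.447 | 0.832 | 1.12 |
| 9 | 1.895 | 0.471 | 0.893 | 1.21 |
| 8 | 1.943 | 0.500 | 0.972 | 1.31 |

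The losses of 2, 3 and 4 subjects are illustrations of scale. The documents do not predict them.

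**6. After the change**

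If the criterion applies only to the fasted condition, it excludes 0 of 12 fed subjects who follow the schedule, whatever their dosing minute.

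**The case against.** The strongest reply is that the criterion was never meant for the fed condition. The two meal criteria mirror the protocol's fasted-condition sentence, 10 hours before and 4 hours after. Read literally, the 10-hour one would exclude every subject, because each eats breakfast 30 minutes before his fed dose. That cannot be intended, so both were probably written with fasting in mind. This is persuasive as to intent, and it supports adding the qualifier. It does not make the qualifier unnecessary. The beverage criterion beside them does mention the fed condition. The 10-hour criterion is plainly unworkable for fed dosing, whereas the 4-hour one could be applied literally, one subject at a time.

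The second reply is that the site can avoid the problem. Both clock times are approximate, so lunch can be held. The liquid ban already discourages lunch before 4 h. Late-dosed fasted subjects must have their lunch held anyway, and each period contains both conditions, so if the sequences run concurrently the site may already be timing lunch to the dose. All of this stands, and it is why the number affected may be zero. Nothing in Protocol 7.4.1, however, tells the site to hold lunch for fed subjects.

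A reader might infer heavy losses. If six fed subjects per period were dosed one after another from 9:00 and all served at 13:00, five of six would fall under 4 h, or 10 of 12 over both periods. The documents do not support that as a forecast: they give no dosing interval, no earliest dose time and no common lunch service. With no stagger the same arithmetic gives 0 of 12 if exactly 4 h does not count.

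A reader might also infer that an early lunch would distort the 4-hour PK sample in fed subjects. The protocol does not prevent lunch from starting before that sample, but nothing in the documents shows that any PK parameter would change.

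**Conclusion.** The mismatch is certain on the text: SAP 7.2 applies a 4-hour post-dose meal exclusion to both conditions, while Protocol 7.4.1 imposes that fast in one. The fed schedule leaves a nominal gap of exactly 4 h, so a compliant fed subject dosed slightly late can meet a mandatory exclusion and lose both periods from the primary comparison.

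The practical effect is uncertain and may be nil. It depends on actual dose and lunch times, and on whether the criterion is applied as written. If 2 to 4 subjects were lost, the interval would widen by about 12% to 31%, assuming an unchanged within-subject SD and n−2 degrees of freedom. The documents do not support a claim that most of the PK set is at risk, or that the food-effect estimate would be biased. This is a wording fault in an analysis-set rule, worth correcting because the correction is nearly free.

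**What to change.** In SAP 7.2, item 5:

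- limit the 4-hour post-dose meal criterion to the fasted condition, where the protocol imposes the fast;
- add the same qualifier to the adjacent 10-hour pre-dose criterion;
- state whether a gap of exactly 4 h counts as a breach.

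SAP 7.2 and Protocol 7.4.1 should then be reconciled so that the analysis set enforces only what the protocol requires. If the sponsor did intend a post-dose food restriction under the fed condition, that belongs in the protocol and is for the sponsor to settle; no meal schedule is proposed here.

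The cost is a few words in the SAP before database lock. Trial conduct and data collection do not change.
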